11.6 Vital Signs

Vital signs include temperature, heart rate, respiration rate, pulse oximetry, and blood pressure. Collection should occur after the patient has been sitting for 3-5 minutes. Vital signs are to be measured at the time points indicated in the applicable Schedules of Events ([Table 2](#) and [Table 3](#) for Stage 2; [Table 4](#) and [Table 5](#) for Stage 3A).

11.7 Electrocardiograms

All patients will have a 12-lead ECG performed during screening.

For patients with MF in Stage 2, during days when pharmacokinetic (PK) samples are drawn (C1 and C2, Infusion 1), an ECG will be performed at 3 distinct time points (triplicates) within 5 minutes (\pm 5 minutes) prior to selected PK sample collections as follows: pre-infusion, and at 30 and 60 minutes post-infusion. An ECG should be performed after the patient is supine for 5 minutes.

11.8 Imaging Studies

After all other entry criteria have been met for an individual patient, a baseline spleen (and liver) volume assessment by MRI or CT scan is required and should be performed within 28 days prior to the first administration of tagraxofusp. Subsequent imaging studies will be performed as indicated in the applicable Schedules of Events ([Table 2](#) and [Table 3](#) for Stage 2; [Table 4](#) and [Table 5](#) for Stage 3A). An abdominal scan is required; evaluation of chest/pelvis may be obtained at the Investigator's discretion.

MRI is the preferred modality as it provides an objective measure of spleen (and liver) volume and does not expose study subjects to ionizing radiation. CT may be used where MRI is not available or suitable for study subjects. Imaging studies will be reviewed locally.

Whenever clinically feasible, it is strongly requested that the same imaging modality at both baseline and subsequent time points be utilized for any given patient throughout their evaluations on-study.

11.9 Cardiac Function: MUGA/2-D Echocardiogram

A MUGA scan or 2-D ECHO to quantify LVEF must be completed during screening within 28 days prior to start of first cycle of study drug. A minimum LVEF is stipulated as a criterion for study inclusion (see [Section 7.1.1](#)).

11.10 Clinical Laboratory Tests

The following assessments should be done at the time points indicated in the applicable Schedules of Events ([Table 2](#) and [Table 3](#) for Stage 2; [Table 4](#) and [Table 5](#) for Stage 3A) and processed by the local laboratory.

- Hematology: Scheduled hematology assessments should at minimum include WBC count, differential WBC (lymphocytes, monocytes, basophils, eosinophils, and neutrophils), RBC count, hematocrit, Hb, platelet count and immature myeloid cells (including blasts + myelocytes + metamyelocytes + promyelocytes + nucleated red blood cells) (for safety assessments as well as for efficacy assessments at the end of each cycle in between bone marrow assessments).
- Serum albumin: May be a component of the serum chemistry panel. See Appendix [Section 18.3](#) for administration of albumin if serum albumin decreases to < 3.0 g/dL during treatment days or in the immediate post-treatment period.
- Serum chemistry and electrolytes: ALT, albumin, alkaline phosphatase (ALP), AST, bicarbonate, bilirubin (total, direct, and indirect), BUN, calcium, chloride, CPK, creatinine, glucose, LDH, magnesium, phosphate, potassium, sodium, total protein, and uric acid.
- Coagulation parameters: PT and/or INR and aPTT.
- Urinalysis (MF patients only): Appearance, color, pH, specific gravity, ketones, leukocytes, protein, glucose, bilirubin, urobilinogen, and occult blood.

Detailed instructions for collecting, processing, storing, and shipping the samples are provided in the Laboratory Manual.

11.10.1 Urine or Serum Pregnancy Test

A urine or serum pregnancy test will be performed locally within 1 week prior to treatment for WOCBP. The pregnancy test should be performed at the clinical research site and processed by the local laboratory.

11.11 Vision Assessment

All patients will be questioned regarding any changes from baseline in visual acuity and/or color vision. Patients who have experienced any \geq Grade 2 study drug-related changes in vision (National Cancer Institute [NCI] Common Terminology Criteria for Adverse Events [CTCAE], v4.03, Grade) will have an ophthalmologic consultation and/or examination performed. In the event any abnormalities are detected, the patient will be followed up as per the recommendations

of the consulting ophthalmologist. Management of treatment-related ocular disorders with inflammatory characteristics should include corticosteroid eye drops and/or other measures, as indicated by an ophthalmologist. In the setting of persistent study drug-related ocular disorders \geq Grade 2, consultation with the study's Medical Monitor is required.

11.12 Tumor Assessments

Tumor assessments must be performed at baseline within 28 days prior to the first administration of tagraxofusp, and on the scheduled specified in [Table 2](#) and [Table 3](#) for Stage 2 and [Table 4](#) and [Table 5](#) for Stage 3A.

Response assessment is performed by means of the following:

- **MF (Stage 2):** The IWG-MRT/ELN 2013 criteria (see [Table 6](#) in Appendix Section 18.1).
- **CMM (Stage 2):** The IWG MDS 2006 criteria (see [Table 7](#) in Appendix Section 18.1).
- **CMM (Stage 3A):** MDS/MPN 2015 criteria (see [Table 8](#) in Appendix Section 18.1).

After Baseline, tumor response assessments are performed at the end of C1 and C4 and then every 12 weeks (± 7 days) thereafter, at End-of-Treatment, and at other timepoints if clinically warranted.

11.12.1 Cytogenetic and Molecular Genetic Testing

Cytogenetic testing should be done on bone marrow aspirate samples and 20 metaphases assessed, when possible. Peripheral blood can be used for the analysis in patients with high circulating blast counts. The number of metaphases counted and analyzed, and abnormal karyotype will be collected in the CRF.

Molecular genetic testing by next-generation sequencing (NGS) will be done on peripheral blood or bone marrow aspirate samples and will be analyzed for the following mutations:

- Patients with MF: *JAK2V617F*, *CALR*, and *MPL*. For 'triple-negative' MF patients, complementary clonal markers, such as *ASXL1*, *EZH2*, *IDH1*, *IDH2*, and *SRSF2* are recommended; additional clonal markers such as *TP53*, *TET2*, *DNMT3A*, and *CBL* are useful for risk-stratification.
- Patients with CMM: *TET2*, *ASXL1*, *DNMT3A*, *EZH2*, *IDH1*, *IDH2*, *BCOR*, *SRSF2*, *U2AF1*, *SF3B1*, *ZRSR2*, *CBL*, *KRAS*, *NRAS*, *NF1*, *JAK2*, *RUNX1*, *SETBP1*, *NPM1*, and *FLT3* are recommended by the ELN/EHA 2018 guidelines for patients being considered for active treatments, including stem cell transplant. Of these genes, an analysis of the following 4 genes is considered mandatory for risk assessment according to accepted risk scoring systems: *ASXL1*, *NRAS*, *RUNX1*, and *SETBP1*.

Detailed instructions for collecting, processing, storing, and shipping the samples are provided in the Laboratory Manual.

11.12.2 Bone Marrow Examinations Including Biological / Target / Correlative Studies

Bone marrow aspirate and biopsy samples will be collected during screening within 28 days prior to the first administration of tagraxofusp and at the end of C1 and C4 and then every 12 weeks (\pm 7 days) thereafter, and at End-of-Treatment. Plasmacytoid dendritic cells (pDCs) and CD123 expression will be assessed by flow cytometry and immunohistochemistry in all bone marrow samples by a central laboratory.

Consult the Laboratory Manual regarding information on the collection, handling, labeling, and shipping of samples.

11.13 Immunogenicity Studies

Peripheral blood samples (10 mL) will be collected (serum red top tube, no additive) for the detection and characterization of tagraxofusp reactive antibodies according to the schedule provided below.

- C1-4: Day 1 (pre-infusion) and Day 21 (\pm 3 days).
- C5 and beyond: End of cycle (D28 [\pm 3 days]).
- End-of-Treatment.
- 30 days after last infusion.
- At least 16 weeks and up to 20 weeks after last infusion.
- If there are clinical manifestations suggesting either an infusion related reaction or drug hypersensitivity, an immunogenicity sample should be obtained, as indicated in [Section 8.2.3.2](#).

Detailed instructions for collecting, processing, storing, and shipping the samples will be provided in the Laboratory Manual.

11.14 Translational Studies/Exploratory assessments

- Flow cytometry: Cells expressing high levels of CD123 have been described in the bone marrow of CML patients and an excess of CD123 expressing pDCs has been shown to correlate with regulatory T cell accumulation and an increased risk of acute leukemia transformation ([Lucas 2019](#)). Additionally, CD14⁺/CD16⁻ monocytes have been indicated to be a specific biomarker that distinguish CML from confounding diagnoses ([Selimoglu-buet 2015](#)). pDCs in addition to leukocyte populations (MF) and monocyte subsets (CML) will be assessed centrally in bone marrow and peripheral blood by flow cytometry. Samples will be collected at the following time points:
 - Screening or C1D1 (pre-infusion)
 - All Cycles: Day 1

- C1: Day 8
- End of Treatment
- Cytokine IL-10: It has been observed that CMML patients with decreased IL-10 expression have poor overall survival when compared to patients with elevated expression of IL-10 ([Niyongere 2019](#)), which suggests that cytokine IL-10 can be a prognostic marker of overall survival ([Niyongere 2019](#)). Peripheral blood samples will be collected for the detection of the cytokine IL-10 for CMML patients at the following time points.
 - C1: Day 1 (pre-infusion) and Day 21 (\pm 3 days)
 - C4: End of cycle (Day 21 [\pm 3 days]).
- In addition to central laboratory analysis of CD123 and monocyte cell populations, an exploratory analysis of CD14 $^+$ /CD16 $^-$ flow cytometry, CYTOF (Mass cytometry), next generation sequencing in CMML patients will be examined at selected sites at the following time points:
 - C1: Day 1 (pre-infusion) and Day 21 (end of cycle)
 - C4: Day 21 (end of cycle)

Detailed instructions for collecting, processing, storing, and shipping the samples will be provided in the Laboratory Manual.

12 Concomitant Medications

12.1 Recommended Medications per Institutional Guidelines/Practices

It is recommended that patients receive the following types of prophylactic therapies/regimens per institutional guidelines/practices:

- Antibacterial: ciprofloxacin, levofloxacin, or an equivalent antibiotic.
- Antifungal: fluconazole, voriconazole, or an equivalent antifungal.
- Antiviral: acyclovir, valacyclovir, or an equivalent antiviral.

12.2 Allowed Medications/Therapies

Refer to [Section 8.2.1.1](#) for premedications to be administered with tagraxofusp.

All patients may receive supportive care measures as clinically indicated, including prophylactic antibiotics, antihistamines, antiemetics, albumin, fluids (hydration), and supportive measures. Patients may receive growth factor support and/or blood product transfusions as per the discretion of their physician.

Albumin 25 g IV daily should be administered if serum albumin is < 3.0 g/dL during days when treatment is withheld or in the immediate post-treatment period. (Refer to [Section 18.3](#) for albumin administration requirements in the setting of elements of CLS.)

Corticosteroid therapy is permitted and is governed by parameters detailed in [Section 12.3](#) (Prohibited Medications/Therapies).

Granulocyte-colony stimulating factor (G-CSF) is permitted only for the treatment of febrile neutropenia. Following a febrile neutropenic event, G-CSF prophylaxis may be considered if there is evidence of response and the Investigator determines that ongoing tagraxofusp treatment is associated with a potentially favorable risk-benefit profile (such a determination should be made in consultation with the Medical Monitor).

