7.1 Patient Selection Criteria

7.1.1 Inclusion Criteria

Patients meeting all of the following criteria may be considered for enrollment:

1. The patient is \geq 18 years old.
2. The patient has a life expectancy of $>$ 6 months.
3. The patient has an Eastern Cooperative Oncology Group (ECOG) performance status (PS) of 0-2.
4. The patient has adequate baseline organ function, including cardiac, renal, and hepatic function:
 - Left ventricular ejection fraction (LVEF) \geq institutional lower limit of normal as measured by multigated acquisition scan (MUGA) or 2-dimensional (2-D) echocardiogram (ECHO) within 28 days prior to start of therapy and no clinically significant abnormalities on a 12-lead electrocardiogram (ECG).
 - Serum creatinine \leq 1.5 mg/dL.
 - Serum albumin \geq 3.2 g/dL (or \geq 32 g/L) in the absence of receipt of IV albumin within the previous 72 hours.
 - Bilirubin \leq 1.5 mg/dL.
 - Aspartate transaminase (AST) and alanine transaminase (ALT) \leq 2.5 times the upper limit of normal (ULN).
 - Creatine phosphokinase (CPK) \leq 2.5 times the ULN.
 - Absolute neutrophil count (ANC) \geq 0.5×10^9 /L.
5. If a woman of child-bearing potential (WOCBP), the patient has a negative serum or urine pregnancy test within 1 week prior to tagraxofusp treatment (intervals shorter than 1 week are acceptable, if required by institutional guidelines).
6. The patient (either male or female) agrees to use acceptable contraceptive methods for the duration of time in the study, and to continue to use acceptable contraceptive methods for 1 week after the last tagraxofusp infusion.
7. The patient has signed informed consent prior to initiation of any study-specific procedures or treatment.
8. The patient is able to adhere to the study visit schedule and other protocol requirements, including follow-up for response assessments.

9. Patient has a 2016 WHO-defined diagnosis of CMML (persistent monocytosis $\geq 1 \times 10^9/L$ for at least 3 months, with other causes excluded, and monocytes $\geq 10\%$ of WBC in peripheral blood, no criteria and no previous history of CML, ET, PV, and acute promyelocytic leukemia; if eosinophilic, neither PDGFRA, PDGFRB, FGFR1 rearrangements nor PCM1-JAK2 translocation; $< 20\%$ blasts in peripheral blood and bone marrow aspirate; > 1 following criteria: dysplasia in > 1 myeloid lineage, acquired clonal cytogenetic or molecular abnormality in hematopoietic cells).

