12.3 Prohibited Medications/Therapies

Prior to discontinuation of tagraxofusp, patients may not receive the following anticancer/antimyeloproliferative agents: JAKi (ruxolitinib, fadaratinib, and others), interferon- α , thalidomide, lenalidomide, cytotoxic chemotherapy agents (including 2-chlorodeoxyadenosine and other purine analogs), hypomethylating agents (5-aza, decitabine and others), tyrosine kinase inhibitors (including those which inhibit the BCR-ABL kinase such as imatinib), HU, and investigational anti-cancer agents.

Patients may not receive additional disease-modifying or cytoreductive agents such as danazol or anagrelide. Patients may not receive erythroid- or platelet-stimulating growth factors.

Hydroxyurea is prohibited during study participation except for cycle 1; Short-term treatment with HU beyond cycle 1 with approval of the Medical Monitor is permitted.

Ongoing corticosteroid therapy at doses of > 20 mg/day prednisone (or equivalent) for > 7 days is not permitted; however transient increases in corticosteroid doses in the setting of infections or other “stress” settings are allowed.

13 Adverse Events and Safety Evaluation

The AE reporting period for a patient treated in the study begins with provision of consent and is continuous through 30 days after the last tagraxofusp infusion. All AEs that occur in treated patients during the AE reporting period must be reported to the Sponsor or designee, whether or not the event is considered related to tagraxofusp. Any known untoward event that occurs beyond the AE reporting period (30 days after the last tagraxofusp infusion) that the Investigator assesses as related to tagraxofusp should also be reported as an AE.

All patients should be monitored for at least 1 hour (or longer at the Investigator’s discretion) following the administration of each tagraxofusp infusion. The Investigator or designated medical staff responsible for study conduct and safety evaluations, should be available during the administration of tagraxofusp and follow-up to assess, treat, or report as necessary any AE or SAE that may occur.

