3.4. Baseline Definitions

For all analyses, baseline will be defined as the most recent measurement prior to the first administration of study drug.

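### Protocol 12.2 leaves growth factors to physician discretion against its own G-CSF limit and 12.3; separately, the neutrophil-response rule does not exclude an ANC sustained by permitted G-CSF prophylaxis

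*Protocol*

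**What the plan says.** **Growth factors.** Protocol 12.2, repeated in the synopsis, says: "Patients may receive growth factor support and/or blood product transfusions as per the discretion of their physician". Later in 12.2: "Granulocyte-colony stimulating factor (G-CSF) is permitted only for the treatment of febrile neutropenia". An exception follows. After a febrile neutropenic event, "G-CSF prophylaxis may be considered if there is evidence of response". A second condition is that "the Investigator determines that ongoing tagraxofusp treatment is associated with a potentially favorable risk-benefit profile". The Medical Monitor is to be consulted on this. No duration is given for this prophylaxis. Protocol 12.3 adds: "Patients may not receive erythroid- or platelet-stimulating growth factors".

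**Neutrophil response.** For Stage 3A, Protocol Table 8 and SAP Table 8-4 list neutrophil response under clinical benefit, which is scored only without progression and without CR or PR. A baseline ANC up to 0.5 × 10⁹/L needs a rise of at least 100% and at least 0.5. A baseline above 0.5 and up to 1.0 needs at least 50% and at least 0.5. Footnote 5 asks for persistence on two analyses spanning 8 weeks or more. It requires hemoglobin and platelets to hold without transfusion, and it mentions cytokine treatment only in the sentence on myeloid precursors and monocytosis.

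**Reporting.** For CMML patients, SAP 4.3.1 presents the number, percentage and time to response for each clinical-benefit component. SAP 3.5 describes the CMML response data as investigator-reported.

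**The concern.** There are two distinct problems, and mending the first does not mend the second.

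The first is wording. A site reading the open sentence alone could think any growth factor is allowed. Once the G-CSF limit and the 12.3 ban are applied, no obvious class of growth factor is left to discretion, so the sentence has no clear function.

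The second is scoring. G-CSF raises the neutrophil count directly. If a patient with a low baseline ANC receives prophylaxis for long enough, the count can meet the Table 8 rule because of G-CSF, and the table would credit the response to tagraxofusp. Stage 3A was set up to examine benefit component by component, so the neutrophil row is itself a result that readers will look at.

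**Working it through.** The plan states no figure on this point, so there is none to reproduce.

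**Step 1: the wording, side by side.** The sentence in 12.2 is unconditional. The later G-CSF sentence and 12.3 are restrictive. The corticosteroid sentence in 12.2 is expressly made subject to 12.3; the growth-factor sentence has no such link. The synopsis repeats both the permission and the limits, so it does not settle the matter.

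**Step 2: the ANC needed (Table 8; b = baseline, × 10⁹/L).**
- b ≤ 0.5: max(2b, b + 0.5) = b + 0.5, because b ≤ 0.5.
- 0.5 < b ≤ 1.0: max(1.5b, b + 0.5) = b + 0.5, because 0.5b ≤ 0.5.

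The absolute rise governs throughout: 0.3 → 0.8, 0.5 → 1.0, 0.8 → 1.3, 1.0 → 1.5. Entry requires an ANC of at least 0.5 (Protocol 7.1.1), but in SAP 3.4 "baseline will be defined as the most recent measurement prior to the first administration of study drug", and hematology is repeated before infusion, so a scored baseline can fall below 0.5.

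**Step 3: can prophylaxis span the persistence period?** 8 weeks = 56 days. In Cycles 1-4, 56/21 = 2.67, so three cycles (63 days) cover it. From Cycle 5, 56/28 = 2 cycles. Nothing in 12.2 stops prophylaxis from running that long.

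**Step 4: does the response condition close the gap?** No. A marrow, spleen or symptom response could satisfy it, and Table 8 scores clinical benefit independently of marrow response. If the prior response is CR or PR, clinical benefit is not scored, which narrows the route.

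**Step 5: how often?** The documents give no rates. As an illustration on assumed inputs, treated as independent: baseline ANC in range 5-20%, febrile neutropenia 5-30%, evidence of response 20-40%.
- Low: 0.05 × 0.05 × 0.20 = 0.0005; 1 − (1 − 0.0005)²⁰ = 1%.
- High: 0.20 × 0.30 × 0.40 = 0.024; 1 − (1 − 0.024)²⁰ = 39%.

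These are chances of at least one candidate in a cohort of 20. On these inputs they overstate the problem, because not every candidate would receive prophylaxis or hold the ANC for 8 weeks. Independence is itself an assumption.

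**Step 6: size of one case (Clopper-Pearson 95% CI).**

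| n | 0 responders | 1 responder | Shift |
|---|---|---|---|
| 20 (planned cohort) | 0-16.8% | 0.1-24.9% | 5 points |
| 15 (assumed) | 0-21.8% | 0.2-31.9% | 6.7 points |
| 10 (assumed) | 0-30.8% | 0.3-44.5% | 10 points |

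Enrollment into Stage 3A was not continued (SAP 5) and the evaluable number is not stated, hence the assumed rows. The shift is 1/n for any misclassified patient. It shows the effect of a case, not its likelihood.

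**The case against.** The case against is substantial. An ordinary reader would let the specific limits override the general sentence, and the synopsis repeats those limits. The scoring issue comes from the prophylaxis exception, not from the open sentence. Several uncommon conditions must coincide, and the analyses are descriptive with no type I error control (SAP 3.7). Stage 3B will not start. All of this stands, and it keeps the point small. It does not supply the missing exclusion in Table 8.

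A reader might infer more than the documents support:
- **That G-CSF would also prolong the reported duration of neutrophil response.** The rebound clause in SAP 4.3.2 concerns stable disease after CR or PR. Component durations are only derived in a similar way, and no rebound rule for neutrophils is written. Table 8's progression footnote 4 disregards therapy-related cytopenia, and Table 7 footnote 3 (Stage 2) tolerates transient cytopenias that recover. Neither is a Stage 3A duration rule, but both make a strict duration rule debatable.
- **That the open sentence contaminates transfusion independence through erythroid agents.** 12.3 prohibits them. Their use would be a protocol violation, which SAP 2.2 already lists.
- **That a case would be almost invisible.** SAP 4.3.8 has no ANC efficacy analysis, but SAP 4.4.3 summarises hematology through Cycle 6 and lists all laboratory data, and SAP 4.4.6 tabulates and lists concomitant medications. What is missing is a rule linking them.

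**Conclusion.** Both parts hold, at low severity. The growth-factor sentence in 12.2 and the synopsis conflicts with the limits around it. Separately, Table 8/8-4 followed exactly would credit a G-CSF-sustained ANC as a neutrophil response.

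The reach is limited. A neutrophil response is scored only without CR or PR, so it does not add to ORR. The Stage 3A activity rule (SAP 3.1.2) rests on spleen volume with symptoms or on transfusion independence. An ANC of at least 1.0 × 10⁹/L is also one item of CR, so the fix should cover it, but every other CR item would have to be met as well. That the event is rare is an inference from the conditions required, not a documented rate. Confidence is medium, mainly because the documents do not report how often G-CSF was used, how many patients are evaluable, or whether anyone remains on treatment.

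**What to change.** 1. **Protocol 12.2 and synopsis**, while any patient remains on treatment. Replace the sentence with: *Blood product transfusions may be given at the physician's discretion; growth factors only as specified below and in Section 12.3.*
2. **SAP 4.3.1**, before database lock. State that ANC values during G-CSF, or within a washout set by the sponsor, do not count toward achieving or verifying neutrophil response or toward the neutrophil item of CR. Keep these patients in the denominator, consistent with how SAP 3.10 treats missing results. Check investigator-reported neutrophil responses against G-CSF dates.

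The cost is one protocol sentence, a short SAP rule and one programmed check. Medication data are already collected throughout the study (Protocol 11.3). The downside is an occasional lost component response: with an assumed 7-day course and an assumed 14-day washout, 7 + 14 = 21 days of ANC values are set aside, about one early cycle. Setting the rule before lock avoids deciding after the fact about an individual responder. The protocol edit has no use once the last patient has stopped treatment.
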